- a. If the subject’s primary study vaccine assignment is known at the time of consent for Study B1971033, the visits in Study B1971033 should be scheduled relative to the last dose of bivalent rLP2086 in the primary study. If the subject’s primary study vaccine assignment is blinded at the time of consent for Study B1971033, the visits in Study B1971033 should be scheduled relative to the last injection of investigational product in the primary study.
- b. Consent may be obtained at Visit 2 if subjects are enrolled at Visit 2.
- c. Vital signs will include blood pressure, pulse rate, and temperature (oral).
- d. Amount of blood collected is approximately 20 mL.

Abbreviations: AE = adverse event; hSBA = serum bactericidal assay using human complement; NDCMC = newly diagnosed chronic medical condition; RRI = research-related injury.

Table 2. Schedule of Activities – Booster Stage

Visit Identifier	Visit 7	Visit 8	Visit 9	Visit 10	Visit 11
	Booster Vaccination	Postvaccination Blood Draw 1	6-Month Telephone Contact	Postvaccination Blood Draw 2	Postvaccination Blood Draw 3
Visit Window	48 Months After Last Dose of Bivalent rLP2086 in Primary Study^a (1396-1484 Days After Last Dose of Bivalent rLP2086, and Within 42 Days After Visit 6)	1 Month After Booster (28-42 Days After Visit 7)	6 Months After Booster (168 to 196 Days After Visit 7)	12 Months After Booster (330-390 Days After Visit 7)	26 Months After Booster (750-810 Days After Visit 7)
Informed consent ^b	X				X
Review eligibility criteria ^c	X				X
Confirm continued eligibility ^c		X	X	X	
Vital signs ^d	X ^e	X		X	X
Medical history	X				
Physical examination	X				
Urine pregnancy test (all female subjects)	X				
Record any nonstudy vaccination and allergen immunotherapy ^f	X ^e	X	X	X	X
Blood sample ^g		X		X	X
IVRS/kit assignment	X				
Investigational product administration and observation	X				
Provide subject or parent/legal guardian with e-diary, caliper, measuring tape/ruler, and thermometer	X				
Record concomitant medications used to treat AEs	X	X	X	X	X
Review e-diary		X			

Table 2. Schedule of Activities – Booster Stage

Visit Identifier	Visit 7	Visit 8	Visit 9	Visit 10	Visit 11
	Booster Vaccination	Postvaccination Blood Draw 1	6-Month Telephone Contact	Postvaccination Blood Draw 2	Postvaccination Blood Draw 3

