4.1.2. Booster Stage

4.1.2.1. Booster Stage Visits 7 to 10

1. Evidence of a personally signed and dated ICD indicating that the subject or subject's parent(s)/legal guardian has been informed of all pertinent aspects for Visits 7 to 10 of the booster stage of the study.
2. Subject continues to meet all Stage 1 inclusion and none of the Stage 1 exclusion criteria.

3. Subject is confirmed as having received bivalent rLP2086 in the primary vaccination study.
4. Subject has completed B1971033 Stage 1 and completed the Visit 6 blood draw.
5. Subject is available for the entire period of the booster stage and the subject or subject's parent(s)/legal guardian can be reached by telephone.
6. Healthy subject as determined by medical history, physical examination, and judgment of the investigator.
7. Male and female subjects of childbearing potential and at risk for pregnancy must agree to use a highly effective method of contraception through Visit 10 of the booster stage. A subject is of childbearing potential if, in the opinion of the investigator, he/she is biologically capable of having children and is sexually active. Refer to [Section 4.5](#) for further information.
8. Negative urine pregnancy test for all female subjects on the day of the booster dose.

4.1.2.2. Booster Stage Visit 11

1. For subject participating in Visit 11, evidence of a personally signed and dated ICD indicating that the subject or subject's parent(s)/legal guardian has been informed of all pertinent aspects of Visit 11.
2. Subject continues to meet all Stage 1 inclusion and none of the Stage 1 exclusion criteria.
3. Subject must have received 2 or 3 doses of bivalent rLP2086 in the primary study on a 0-, 2-, and 6-month or a 0- and 6-month schedule.
4. Subject must have completed booster vaccination at Visit 7.

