9.3. Immunogenicity Analysis Populations

Only subjects who were compliant with primary study eligibility criteria while enrolled in the primary study will be included in this study. Therefore, the modified intent-to-treat (mITT) population will be used for Stage 1 immunogenicity analyses. The Stage 1 mITT population will include subjects who have at least 1 valid and determinate assay result in Stage 1 of Study B1971033.

In general, the evaluable population will include all subjects who were eligible, received all investigational products, had blood drawn for assay testing within the required time frames, had valid and determinate assay results for the proposed analysis, and had no important protocol deviations. A major protocol deviation is one that, in the opinion of the sponsor's global medical monitor, would materially affect assessment of immunogenicity, eg, subject receipt of a prohibited vaccine or medication that might affect immune response or a medication error with suspected decrease in potency of the vaccine. For booster stage time points (Visits 7, 8, 10, and 11), the primary immunogenicity analysis will be based on the evaluable population (for summaries including Visit 11 for the subset of subjects of the evaluable population who participated in Visit 11). Booster stage immunogenicity analyses will also be performed for the booster stage mITT population (for summaries including Visit 11 for the subset of subjects of the booster stage mITT population who participated in Visit 11), which will include subjects who received the booster vaccination and who have at least 1 valid and determinate assay result.

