5.2. Immunogenicity Analysis Set

Only subjects who were compliant with primary study eligibility criteria while enrolled in the primary study will be included in this study. Therefore, the modified intent-to-treat (mITT) population will be used for Stage 1 immunogenicity analyses. The mITT population will include subjects who have at least 1 valid and determinate assay result in Stage 1 of Study B1971033.

For booster stage time points, the primary immunogenicity analysis will be based on the evaluable population. For analyses including the 26 months postbooster vaccination time point, the analyses will use the subset of evaluable population for Booster stage who proceed to Visit 11.

The evaluable population includes subjects who:

[REDACTED]

1. Are eligible for the study (i.e., meet all Stage 1 and Booster Stage eligibility criteria).
2. Have received the scheduled investigational product as intended.
3. Have a prevaccination blood drawn prior to the booster vaccination, and have a postvaccination blood draw within 28-42 days after the booster vaccination.
4. Have valid and determinate assay result for the proposed analysis.
5. Have received no prohibited vaccines or treatment.
6. Have no other major protocol violations as determined by the sponsor's global medical monitor.

For above listed items, 1 through 4 will be computerized checks of the data, while items 5 and 6 will be determined by clinical review. A major protocol violation is a protocol violation that, in the opinion of the sponsor's global medical monitor would materially affect assessment of immunogenicity, e.g, subject receipt of a prohibited vaccine or medication that might affect immune response or a medication error with suspected decrease in potency of the vaccine. The global medical monitor from the sponsor will identify those subjects with protocol violations before any immunogenicity analysis is carried out.

Booster stage immunogenicity analyses will also be performed for the mITT population, which will include subjects who received the booster vaccination and who have at least 1 valid and determinate assay result in the booster stage. For analyses including the 26 months postbooster vaccination time point, the analyses will use the subset of mITT population for Booster stage who proceed to Visit 11.

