7. HANDLING OF MISSING VALUES

7.1. Immunogenicity Data

The primary immunogenicity analyses for the study will be based on the observed, determinate observations, which is under the assumption of missing completely at random (MCAR (Scott and Hsu)¹). Missing data will not be imputed for analysis. As a sensitivity analysis, a mixed-effects model with repeated measurements (MMRM) will be utilized for the immunogenicity analysis, which assumes the missingness is at random (MAR).

The hSBA LLOQ are listed in Table 8.

Table 8. LLOQ for hSBA

Strain	LLOQ
CCI [REDACTED]	1:16
CCI [REDACTED]	1:8
CCI [REDACTED]	1:8
CCI [REDACTED]	1:8

For the calculation of GMT, values below the LLOQ will be set to 0.5*LLOQ for the primary analysis.

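### SAP 5.2 ties the booster evaluable set to the Visit 8 draw window alone, so valid on-time 12- and 26-month titers can leave the primary analysis while the Visit 10 and 11 windows go unchecked

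*SAP*

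**What the plan says.** SAP 5.2 sets the primary population: "For booster stage time points, the primary immunogenicity analysis will be based on the evaluable population". It lists six conditions. Item 3 asks for a blood draw before the booster and that subjects "have a postvaccination blood draw within 28-42 days after the booster vaccination". Item 4, by contrast, asks for a valid result for whichever analysis is being done. Items 1 to 4 are applied by program, and items 5 and 6 by clinical review. SAP 8.2.1 uses this population at Visits 8 and 10, and its Visit 11 subset for analyses that include Visit 11. No evaluable set is defined per visit.

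Protocol Table 2 gives three post-booster draw windows:
- Visit 8: "1 Month After Booster (28-42 Days After Visit 7"
- Visit 10: "12 Months After Booster (330-390 Days After Visit 7"
- Visit 11: "26 Months After Booster (750-810 Days After Visit 7"

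Protocol 9.3 describes the evaluable population more generally. Blood must be drawn within the required time frames (plural, no visit singled out), and subjects must have "had valid and determinate assay results for the proposed analysis". Protocol 4.1.2.2 lists four criteria for Visit 11: consent, continued Stage 1 eligibility, an eligible primary schedule, and "Subject must have completed booster vaccination at Visit 7". A Visit 8 draw is not among them.

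SAP 7.1 states that the primary immunogenicity analyses "will be based on the observed, determinate observations", without imputation.

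**The concern.** The condition works in the wrong direction for the later visits. A subject can be boosted, miss the Visit 8 window, meet the Visit 11 criteria, consent again and give a valid on-time sample at 26 months. The program check on item 3 then removes that titer from the primary 26-month estimate. The date of the 1-month draw does not make a 12- or 26-month titer invalid. Meanwhile a subject with an on-time Visit 8 draw and an off-window Visit 10 or 11 draw passes item 3, because those windows appear nowhere in the list.

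At stake are some avoidable loss of precision at the visit with the fewest expected subjects, and a primary 12- and 26-month set selected partly on punctuality at one month.

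**Working it through.** The documents give no figure to reproduce: no expected rate of missed or off-window Visit 8 draws, no power and no statistical sample-size basis (Protocol 9.1). The check is a reading of the rule, followed by an illustration of its size.

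**Step 1. Apply the rule.**

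| Subject (boosted, otherwise compliant) | Item 3 | Primary at Visits 10 and 11 |
|---|---|---|
| Visit 8 missed or off window; Visits 10 and 11 on time and valid | fails | excluded |
| Visit 8 on time; Visit 10 or 11 off window but valid | passes | included, unless removed on clinical review |

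The rule in Protocol 9.3, applied visit by visit, would give the opposite result in both rows.

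**Step 2. Window lengths (Protocol Table 2).** Visit 8: 42 - 28 + 1 = 15 days. Visit 10: 390 - 330 + 1 = 61 days. Visit 11: 810 - 750 + 1 = 61 days. The only window enforced is the shortest. Protocol 4.4 delays a draw after recent systemic antibiotics, and Protocol 6.3.2 applies that check at Visit 8, so a compliant subject could be pushed past day 42. Width alone does not establish how often this happens.

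**Step 3. Precision.** Inputs: at most 200 subjects at Visit 11 (Protocol 3.4); exact two-sided 95% intervals (SAP 8.1.2). Assumed: 2%, 5% or 10% without an on-window Visit 8 draw, a 60% response, and all 200 Visit 11 titers valid and on time. For r responders among n, the limits are the 0.025 quantile of Beta(r, n - r + 1) and the 0.975 quantile of Beta(r + 1, n - r). This is equivalent to the SAP's F-distribution form.

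| Share dropped | Titers dropped per strain | n left | Half-width, points |
|---|---|---|---|
| 0 | 0 | 200 | 7.00 |
| 2% | 200 × 0.02 = 4 | 196 | 7.06 |
| 5% | 200 × 0.05 = 10 | 190 | 7.18 |
| 10% | 200 × 0.10 = 20 | 180 | 7.38 |

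(At n = 196, r is rounded to 118.) For a single schedule group of an assumed 100 subjects, a 10% loss moves the half-width from 9.97 (n = 100) to 10.53 (n = 90).

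**Step 4. Shift in the estimate.** If a share m is excluded, the kept proportion minus the full proportion equals m × (kept response - excluded response). With m = 10% and an assumed 10-point difference, the shift is 0.10 × 10 = 1.0 point. Nothing in the documents says that such a difference exists.

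**The case against.** The best defence is that one anchored cohort is useful. The booster endpoint is a series (after the primary course, before the booster, then 1, 12 and 26 months), and item 3 ensures that everyone counted at 12 or 26 months also has a pre-booster draw and an on-time 1-month draw. That nesting is a real benefit and is lost under a per-visit rule. But neither document gives it as the reason, and item 3 does not deliver a common cohort. Item 4 and the observed-case approach already let n vary by visit, and Visit 11 does not require a Visit 10 draw.

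Second, the titers are still reported. The booster-stage mITT analysis needs only one valid booster-stage result, and the repeated-measures model in SAP 8.2.3 runs on the mITT population. This stands and limits the weight of the point, but neither is the primary analysis.

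Third, on one reading of the plural time frames in Protocol 9.3, an off-window Visit 8 draw already fails the protocol's own definition. That reading is possible, so this is a poor fit and not a flat contradiction. It would still require the Visit 10 and 11 windows to be checked as well, which the SAP list does not do.

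A reader might also infer that the 26-month estimate is biased, that the Visit 8 draw is irrelevant to later visits, or that the booster is the only condition for Visit 11. The documents support none of these. Nothing links Visit 8 punctuality to later titers; Visit 8 follows the same booster and belongs to the same series; and Visit 11 has four criteria.

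**Conclusion.** The point holds as a drafting flaw with small consequences. As written, the primary 12- and 26-month estimates exclude some valid, on-time titers because of the Visit 8 draw, and apply no window of their own. On the assumptions above, the loss at Visit 11 is 4-20 titers per strain and 0.1-0.4 points of half-width. The net recovery would be smaller by any titers that then fail their own visit's window. The 2-10% rate and the 60% response are assumptions; only the ceiling of 200 comes from the protocol. The study is descriptive with no hypothesis test, so power and type I error are not affected. This is worth correcting because it is cheap, not because it threatens the conclusions.

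**What to change.** Replace the single booster-stage definition in SAP 5.2 with one per time point. For each visit's estimate require:

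- items 1, 2, 5 and 6 as they stand;
- the pre-booster draw (completing the Visit 6 draw is already a booster entry criterion in Protocol 4.1.2.1);
- a valid, determinate result from that visit's own draw, taken within that visit's protocol window after Visit 7: 28-42 days for Visit 8, 330-390 for Visit 10, 750-810 for Visit 11.

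Do not require an on-window Visit 8 draw for the Visit 10 and 11 estimates. Keep the own-visit window in the rule: removing item 3 without it would admit off-window draws and move the SAP further from Protocol 9.3. Update SAP 8.2.1 to match. If a within-subject series is wanted, add a supportive table of subjects with all draws on time. If a Visit 8-anchored cohort is in fact intended, say so, give the reason and align the text with Protocol 9.3.

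The cost is SAP wording and one flag per visit; SAP 8.2.5.1 already tabulates draws before, within and after each window. The downside is that contributors at later visits are no longer nested in one Visit 8-anchored set, and n differs slightly more between visits.

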5.3. Safety Analysis Set

The safety population for Stage 1 of the study will include all subjects who have at least 1 blood draw in the study. The safety population for the Booster Stage will include all subjects who received the booster vaccination and for whom safety data are available. For analyses including the 26 months postbooster vaccination time point, the analyses will use the subset of safety population for Booster stage who proceed to Visit 11.

5.4. Other Analysis Sets

Not applicable.

5.5. Treatment Misallocations

Treatment in this study is restricted to the Booster Stage. Subjects enrolled to the Booster Stage but not vaccinated will be excluded from the mITT immunogenicity population and safety analyses. Subjects vaccinated during the Booster Stage but not enrolled will be excluded from immunogenicity analyses but included in the safety population.

5.6. Protocol Deviations

The following describes any protocol deviations that relate to the statistical analyses or populations:

5.6.1. Deviations Assessed Prior to Enrollment

Subjects who do not meet the inclusion / exclusion criteria will not be included in the Booster Stage evaluable immunogenicity population as specified in [Section 5.2](#).

5.6.2. Deviations Assessed Post-Enrollment

The full list of protocol deviations (including protocol violations) for the study report(s) will be compiled prior to database closure for the first interim analysis. The subjects with major protocol deviations, as determined by Medical Monitor, will be excluded from the Booster Stage evaluable immunogenicity population.

6. ENDPOINTS AND COVARIATES

6.1. Immunogenicity Endpoints

The 4 primary test strains for hSBA testing are CCI (A22 variant), CCI (A56 variant), CCI (B24 variant), and CCI (B44 variant). The lower limit of quantitation (LLOQ) for CCI (A22) is an hSBA titer equal to 1:16. The LLOQ for the other 3 primary test strains is an hSBA titer equal to 1:8.

hSBA assays using the 4 primary test strains will be conducted using sera obtained at Visits 1 to 6 from all subjects entered into stage 1, including subjects who did not receive bivalent rLP2086 in the primary study (B1971015 Group 2).

6.1.1. Primary Immunogenicity Endpoints

Stage 1

- *Proportion of subjects with hSBA titers \geq LLOQ for each of the 4 primary strains, at each blood draw visit in Stage 1 (Visits 1-6).*

Booster Stage

Proportions of subjects with hSBA titers \geq LLOQ for each of the 4 primary strains at 1 month following the last vaccination received in the primary study, before the booster vaccination (Visit 6), and 1 month, 12 months, and 26 months (Visits 8, 10, and 11) following booster vaccination.

CCI

CCI

- *Percentages of subjects reporting systemic events via the e-diary by type (fever, vomiting, diarrhea, headache, fatigue, chills, muscle pain other than muscle pain at the injection site, and joint pain) and by severity after a booster vaccination of bivalent rLP2086.*
- *Percentage of subjects reporting the use of antipyretic medication via the e-diary after a booster vaccination of bivalent rLP2086.*
- *Percentages of subjects with at least 1 AE occurring during the following time periods:*
 - *From Visit 7 to Visit 8*
- *Percentages of subjects with at least 1 SAE during the following periods:*
 - *From Visit 7 to Visit 8*
 - *From Visit 8 to Visit 9*
 - *From Visit 7 to Visit 9*
- *Percentages of subjects with at least 1 NDCMC occurring during the following time periods:*
 - *From the 6-month safety telephone call in the primary study to Visit 6 (Stage 1)*
 - *From Visit 7 to Visit 8*
 - *From Visit 8 to Visit 10*
 - *From Visit 7 to Visit 10*
 - *From Visit 8 to Visit 11 (only subjects proceeding to Visit 11)*
 - *From Visit 7 to Visit 11 (only subjects proceeding to Visit 11)*
- *Percentages of subjects with at least 1 medically attended event occurring during the following time periods:*
 - *From Visit 7 to Visit 8*
 - *From Visit 8 to Visit 9*
 - *From Visit 7 to Visit 9*
- *Percentage of subjects reporting at least 1 immediate AE after receiving the booster dose of bivalent rLP2086.*
- *Numbers of days subjects miss school or work because of AEs from Visit 7 through Visit 9.*

CCI [REDACTED]

CCI [REDACTED]

[REDACTED]

[REDACTED]

[REDACTED]

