3. STUDY DESIGN

3.1. Description

Stage 1 of the study (Visits 1-6) is designed to provide follow-up information on Pfizer Studies B1971010, B1971012, and B1971015 (see [Table 4](#)), which used the final formulation and dose of bivalent rLP2086. For the purpose of this study, these 3 studies are referred to as the primary studies. All subjects enrolled in Study B1971033 were originally enrolled in one of these studies. In Stage 1, subjects will attend up to 6 study visits for collection of a 20-mL blood sample at each visit (see [Table 5](#)).

The booster stage of the study (Visits 7 to 11) is optional for eligible subjects at selected sites. Subjects who wish to participate in the booster stage must have completed Stage 1 and received all scheduled doses of bivalent rLP2086 in the primary study. Subjects will be required to sign a consent form to enter and participate in the booster stage for Visits 7 to 10. Eligible subjects at selected sites will be asked to sign another consent form prior to participating in Visit 11 for a blood draw at 26 months after the booster vaccination.

For consenting booster stage subjects, a booster dose of 120 µg of bivalent rLP2086 will be administered at Visit 7 and blood samples (20 mL per visit) will be collected for immunogenicity analysis 1 month, 12 months, and 26 months after the booster vaccination (Visits 8, 10, and 11) (see [Table 5](#)).

Table 5. Study Design Overview

	STAGE 1						BOOSTER STAGE				
Visit purpose	Blood draw	Booster vaccination	Blood draw	6-Month telephone contact	Blood draw	Blood draw					
Visit number	1	2	3	4	5	6	7	8	9	10	11
Approximate month	6	12	18	24	36	48	48	1 Month after booster	6 Months after booster	12 Months after booster	26 Months after booster
Vaccination							Bivalent rLP2086				
Blood draw	20 mL		20 mL		20 mL	20 mL					

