9.5. Safety Analysis

The safety population will be used for all safety analyses. For Stage 1 time points, the safety population will include all subjects who have at least 1 blood draw in the study. For the booster stage, the safety population will include all subjects who have received the booster vaccination and for whom safety information is available. Missing safety data will not be replaced or imputed. For summaries that include Visit 11 or after Visit 10, the subset of subjects of the safety booster population who participated in Visit 11 will be used.

The proportion of subjects reporting local reactions at the investigational product administration site and systemic events and use of antipyretic medication within the 7-day period after the booster vaccination will be descriptively summarized. Severities of local reactions and systemic events reported after vaccination will also be descriptively summarized. Two (2)-sided exact 95% CIs will be presented with the proportions.

All of the AEs and RRIIs will be categorized according to the Medical Dictionary for Regulatory Activities (MedDRA) and will be summarized. A medically attended event is defined as a nonserious AE that results in an evaluation at a medical facility. An NDCMC is defined as a disease or medical condition not previously identified that is expected to be persistent or otherwise long-lasting in its effects. All summaries will show the number and percentage of subjects experiencing at least 1 event and the number of events. Two (2)-sided exact 95% CIs will also be presented for the percentages.

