6.2.4.1. Analysis Intervals

There will be up to 6 analysis intervals for safety data collected via case report form (CRF).

Table 7. Analysis Intervals for AE, SAE, Medically Attended Events (MAEs) and Newly Diagnosed Major Conditions (NDCMC)

#	Analysis Interval	Analysis Population	Interval Start date (inclusive)	Interval Stop (inclusive)	Safety Data
1	Stage 1	Stage 1 Safety	Enrollment	Visit 7 date – 1 day	NDCMC, AE
2	Vaccination Phase	Booster Stage Safety	Booster vaccination date (Visit 7)	Visit 8 date – 1 day	AE, SAE, MAE, NDCMC
3	Follow-up Phase	Booster Stage Safety	Visit 8 date	Visit 9 date (Visit 10 date for NDCMC)	SAE, MAE, NDCMC
4	Throughout the Booster Stage	Booster Stage Safety	Booster vaccination date (Visit 7)	Visit 9 date (Visit 10 date for NDCMC)	SAE, MAE, NDCMC, autoimmune and neuroinflammatory conditions, Days missed school/work
5	Throughout the Extended Booster Stage	Booster Stage Visit 11 Subset	Visit 7 date	Visit 11	NDCMC
6	Extended Follow-up Phase	Booster Stage Visit 11 Subset	Visit 8 date	Visit 11	NDCMC

AE = Adverse Events, SAE = Serious Adverse Events, MAE = Medically Attended Events, NDCMC = Newly Diagnosed Chronic Medical Conditions

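### The 26-month post-booster chronic-condition percentages count only subjects who reach Visit 11, and a new chronic condition can itself affect who gets there

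*SAP*

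**What the plan says.** The primary safety endpoints (Protocol Section 2.2.2; SAP Section 6.2.1) include the percentage of subjects with at least one NDCMC over several intervals. The Visit 7 to 8, Visit 8 to 10 and Visit 7 to 10 rows carry no attendance condition; the last reads simply "From Visit 7 to Visit 10". The two rows that run to month 26 do carry one: "From Visit 7 to Visit 11 (only subjects proceeding to Visit 11", and likewise from Visit 8.

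SAP Table 7 (Section 6.2.4.1) gives the populations. Intervals 5 and 6, the two that end at Visit 11, use the "Booster Stage Visit 11 Subset". Intervals 3 and 4 use the full Booster Stage safety population and stop at "Visit 9 date (Visit 10 date for NDCMC". SAP Section 5.3 defines that full population: "The safety population for the Booster Stage will include all subjects who received the booster vaccination and for whom safety data are available". For the 26-month time point it narrows it: "the analyses will use the subset of safety population for Booster stage who proceed to Visit 11". Protocol Section 9.5 has the same rule in slightly different words: "the subset of subjects of the safety booster population who participated in Visit 11 will be used".

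On entry to Visit 11, Protocol Section 3.1 states: "Eligible subjects at selected sites will be asked to sign another consent form prior to participating in Visit 11". Protocol Section 4.1.2.2 requires the Stage 1 criteria still to be met and restricts Visit 11 to the 0,2,6-month and 0,6-month schedules. Protocol Section 3.4 expects up to 200 subjects there. SAP Section 8.2.4.2.2 confirms that NDCMC collection ends at Visit 10 for everyone outside the Visit 11 subset.

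**The concern.** The two 26-month intervals begin at the booster or one month after it, but their population is fixed about two years later. Membership then depends on something that the outcome can change.

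The documents show how. Stage 1 exclusion 3 (Protocol Section 4.2.1), re-applied at Visit 11, covers a severe chronic condition that the investigator judges makes the subject unsuitable. Protocol Section 6.5 names neuroinflammatory and autoimmune conditions among the adverse events that may lead to withdrawal; if new and lasting, they would also be NDCMCs. Protocol Section 4.5 says Visit 11 was added after subjects had completed Visit 10, so the separate decision to take part comes largely after earlier NDCMCs are known.

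At stake is the only primary safety endpoint that covers the whole period to month 26. Active collection of serious and medically attended events stops at Visit 9. Following safety to 26 months is one of the stated purposes of the amendment (Protocol Section 1.2.5).

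**Working it through.** The study is descriptive and its sample size has no statistical basis (Protocol Section 9.1), so there is no plan figure to reproduce. The check has two parts.

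**1. Where an event is counted.** Take a boosted subject on an eligible schedule who does not reach Visit 11.

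| NDCMC onset | Visit 7-10 row, and 7-8 or 8-10 | Visit 7-11 row (and 8-11 if onset is from Visit 8) |
|---|---|---|
| Visit 7 to Visit 10 | Counted (full Booster Stage safety population) | Subject absent from numerator and denominator |
| After Visit 10 | Outside the interval | Not routinely collected |

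A condition starting in month 3 is thus reported in the Visit 8-10 and 7-10 rows and is missing only from the 26-month rows. A condition starting after Visit 10 is uncollected rather than recorded and set aside.

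**2. How far the Visit 7-11 percentage could move.** The only documented input is 200 attenders (the planned maximum). The rest are assumptions:
- attenders' NDCMC risk, p = 1% or 2%
- eligible boosted subjects who do not attend, m = 10, 25 or 50
- their risk as a multiple of p, k = 1, 3 or 5.

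All-eligible percentage = (200p + m·k·p) / (200 + m).

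| m | p | k | Calculation | All eligible | Shift (points) | Expected subjects with an NDCMC left out |
|---|---|---|---|---|---|---|
| any | any | 1 | – | p | 0 | m·p (0.1 to 1.0) |
| 10 | 1% | 5 | (2 + 0.5)/210 | 1.19% | 0.19 | 0.5 |
| 25 | 2% | 3 | (4 + 1.5)/225 | 2.44% | 0.44 | 1.5 |
| 50 | 1% | 5 | (2 + 2.5)/250 | 1.80% | 0.80 | 2.5 |
| 50 | 2% | 5 | (4 + 5)/250 | 3.60% | 1.60 | 5.0 |

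Over the full grid the shift is 0 to 1.6 points, and 0.1 to 5.0 subjects with an NDCMC are left out.

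A second view lets attendance depend on the outcome. With true risk P, attendance a1 in subjects with an NDCMC and a0 in those without, the reported percentage is P·a1 / (P·a1 + (1 − P)·a0). Assume P = 6% and a0 = 60%:
- a1 = 50%: 0.030/(0.030 + 0.564) = 5.05%
- a1 = 40%: 0.024/(0.024 + 0.564) = 4.08%
- a1 = 30%: 0.018/(0.018 + 0.564) = 3.09%
- a1 = 60%: 6%, no bias
- a1 = 70%: 0.042/(0.042 + 0.564) = 6.93%, bias upward.

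For scale, the exact 95% CI with n = 200 is 0.12% to 3.57% for 2 events, 0.55% to 5.04% for 4 events and about 1.1% to 6.4% for 6 events.

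**The case against.** A reader might infer that conditions already recorded in non-attenders are thrown away. The documents do not support that. The Visit 7-8, 8-10 and 7-10 rows count them, and SAP Section 8.2.4.2.2 also tabulates NDCMCs by preferred term over the booster stage. Nor is this the longest safety interval in the trial: the Stage 1 NDCMC endpoint runs from the 6-month call in the primary study to month 48, about 42 months. Visit 7-11 is the longest post-booster interval.

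The strongest defence is that the restriction is openly stated and has a reason. Only Visit 11 attenders are routinely followed for NDCMCs to month 26, and a crude percentage over all boosted subjects would mix 12-month and 26-month follow-up. Much non-attendance is structural, because only two schedules qualify and only selected sites take part. The assumed bias also lies within sampling error in every scenario shown.

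Most of this stands. It means the attendee percentage should stay and that the right comparison group is boosted subjects on the eligible schedules, not everyone boosted. It does not remove selection among those eligible subjects. The Visit 7-10 row cannot stand in for the 26-month estimate, because its denominator differs: the 26-month percentage could even come out below the 12-month one, which cannot happen for cumulative incidence in a single cohort. The exact CI does not help either, since it measures sampling error and takes no account of who attends.

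**Conclusion.** The point holds for the Visit 7-11 and Visit 8-11 NDCMC rows only. They describe subjects who reached Visit 11, and a new chronic condition can affect whether a subject does. Eligible non-attenders with an NDCMC by Visit 10 are missing from the 26-month estimate, though not from the 12-month one.

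The bias is most plausibly downward, because the eligibility re-check and adverse-event withdrawal both work against ill subjects. Its direction is not proven: equal attendance gives none, and higher attendance by subjects with an NDCMC reverses it. Its size cannot be determined from the documents. The shift of 0 to 1.6 points rests on assumed risks, numbers of non-attenders and risk ratios; the 3.1% to 6.9% range around a true 6% rests on an assumed risk and assumed attendance. Neither is an estimate for this trial. The change is worth making because it is cheap and concerns a primary safety endpoint, not because a large error has been shown.

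**What to change.** - Keep the protocol-specified percentages for Visit 7-11 and 8-11, and label them in the SAP and tables as conditional on Visit 11 participation.
- Add to the SAP a Kaplan-Meier cumulative percentage of first NDCMC, with 95% CI, from Visit 7 and from Visit 8 to Visit 11. Use all boosted subjects in the groups scheduled for Visit 11, censored at each subject's last NDCMC contact. An event recorded by Visit 10 then counts whether or not the subject later attends.
- Define those groups. Protocol Section 4 uses the two primary-series schedules; SAP Section 2 names B1971012 Groups 2 and 3. The SAP should say which applies.
- Show the Visit 7-10 NDCMC percentage separately for eligible attenders and eligible non-attenders. This is the direct check on whether selection occurred.
- Use one term for the subset. The protocol refers to participation in Visit 11, the SAP to proceeding to it.

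The cost is SAP wording and one or two extra tables from data already collected. A Kaplan-Meier percentage reads less simply than a crude one. The remedy is also partial: the month 12 to 26 portion still comes only from Visit 11 participants, so informative censoring after Visit 10 remains and should be stated as a limitation.
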